specifically compare the gut microbiota composition of prediabetes subjects who exhibited improved glucose metabolism following the WWB diet with those who responded least to this dietary intervention to determine if differences in gut bacteria could explain the beneficial effect of WWB in some individuals.

III. Anticipated Results

We expect to achieve >95% compliance (based on in-house observations of test meal consumption, returned foods, and circulating biomarkers of WWB intakes, e.g., alkylresorcinol concentrations of 19:0, 21:0, and 23:0) without any adverse effects or changes in body mass or energy intakes.

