Based on prior studies,¹³ we expect a >25% within-trial decrease in postprandial blood glucose by WWB in high-responders compared to WB. While a statistically significant between-treatment effect is also expected, our study is designed to define ‘high-responders’ vs ‘low-responders’ towards precision nutrition rather than achieve group mean differences by bread treatment.¹⁴ In addition, we expect reduced serum endotoxin during WWB intervention, as metabolic endotoxemia is known to initiate insulin resistance in obese persons.^{41, 42} These benefits are expected to occur through an anti-inflammatory mechanism that attenuates gut-derived endotoxin translocation⁴³ or an antimicrobial activity of WWB that depletes pyrogenic Gram-negative bacteria. In support of the former, we expect WWB will decrease small intestinal and colonic permeability,⁴⁴ based on decreased urinary excretion of lactulose/mannitol and sucralose/erythritol. WWB may also alter, at least in a subset of the study participants, the gut microbial composition, as reported previously in both healthy adults as well as in persons with MetS (e.g. an increase of *Lachnospira*, *Faecalibacterium*, *Prausnitzii*, and *Prevotella copri* abundance and a decrease in *Enterobacteriaceae* abundance in the WWB group^{45, 46}). It is also possible to detect selective antimicrobial activities of WWB (possibly due to its rich phytochemicals)^{16, 47} and consequentially decreased LPS-producing Gram-negative bacteria. If these findings are consistent in a subset group of study participants who have larger changes of glycemic response post WWB intervention, they will collectively suggest a mechanism, at least in part, that the multi-facet health benefit of WWB consumption is gut microbiome-dependent. Meanwhile, with our combined targeted and untargeted metabolomics approaches, we expect a group of known (e.g., energy metabolism metabolites and amino acids)^{48, 49}, and unknown metabolic features may change significantly in fecal and blood metabolome between WWB and WB intervention. Taken together, these studies will establish a solid foundation for determining health and metabolic effects on the human host based on the composition and microbial metabolic capability of gut microbes.

IV. Pitfalls and Alternatives

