Recruitment. We acknowledge the challenge to recruit adults with prediabetes for a nutrition study during this unusual time of pandemic. Consistent with our previous studies,⁵⁰⁻⁵² we will consult the recruitment office of the OSU CCTS for assistance. They maintain a participant database (>126K registrants) and provide marketing support for study recruitment (e.g. social media, printed flyers, e-newsletters reaching ~100K faculty/staff and students at OSU).

[figure not shown]
All proposed procedures are well-established and frequently utilized by our research team. We, therefore, do not expect potential technical problems. However, we acknowledge the challenge of the potential interpersonal variability of dietary responses to WWB among the enrolled study participants, and there may be difficulties to identify sufficient “high-responders” and “low-responders” based solely on the glycemic responses. If needed, we will combine other health parameters, such as HOMA-IR, serum endotoxin, and select inflammatory biomarkers, to define response indicators for their gut microbiome dependency.

V. Significance of the Research and Potential Benefits

Whole grain, especially whole wheat food, is a recognized, important part of healthy dietary patterns due to its high abundance of fibers, protein, and bioactive phytochemicals. However, from both clinical trials and observational studies, controversy persists to clearly define the advantage of having incorporating whole wheat into the diet to manage metabolic disorders including prediabetes. Gut microbial composition and their metabolism, as recently emerged in many exciting studies, may play a critical role in determining the health benefits of having whole wheat in a regular diet in diverse populations. Therefore, our study is **significant** because it will provide critical data to help resolve the controversy by studying the gut microbiome-mediated, personalized effects of whole wheat intake in persons with prediabetes. Specifically, the integration of our multi-omics workflow coupled with studies in humans and in vitro will advance an understanding of the metabolic signatures of gut bacteria function to control the risk of prediabetes/glucose intolerance

VI. Procedures

A. Overview of Study Design

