We plan to conduct a 2x2 *randomized, controlled, crossover trial* in persons with prediabetes (n = 40; 1:1 M/F) to assess 2-wk consumption of white bread (WB) vs whole wheat bread (WWB) on cardiometabolic and gut microbiome parameters (Figure 1). Participants will be recruited from the Columbus, OH area,

consistent with earlier successful studies conducted by the [name] lab. Participants will be block-randomized in 4-unit blocks to receive WB or WWB (128 g/day; 4 bread slices/d, according to the USDA “My Plate” recommendation and other similar studies)^{14, 53, 54} for 2-wks. During each study arm, participants will be provided standardized test meals containing WB or WWB, these foods will be prepared and packaged in the Human Nutrition Metabolic Research Kitchen (Evans Laboratory) to be devoid of whole grain products, probiotic-containing foods (e.g., yogurt), or fermented foods that are known to alter gut bacteria populations. Before and after each 2-wk study arm, a fasting blood sample will be obtained for metabolomic and clinical measures. Blood pressure and anthropometrics also will be assessed on days 1, 7, 14, and participants will collect a fecal sample to provide to the study team during their visits on day 1 and day 14. Lastly, on day 14, participants will simultaneously complete an oral glucose tolerance test and gut permeability test, which involves ingesting a glucose solution that also contains non-digestible sugar probes prior to collecting complete 24-hour urine samples for assessments of upper and lower gut permeability (described below). Upon completing these procedures, participants will undergo >2-weeks wash-out before repeating the study identically, but with crossover to the alternate bread diet.

B. Study Subjects

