2. Recruitment. We will recruit participants through posted flyers, e-mail, electronic and newsprint advertisements (e.g. campus student and faculty/staff newspapers, local and regional newspapers; see attachment “*Advertisements*”), and word of mouth. The posted advertisements will instruct interested participants to call the study center ([name] Laboratory, Department of Human Sciences) or complete an online pre-screening survey to obtain further information. During the phone-in hours, a trained individual (i.e. project coordinator or graduate assistant) will be available to describe the study and determine preliminary qualification by conducting a scripted phone interview (e.g. do you take dietary supplements?, do you smoke?; see “*Phone Script*” attachment). The individual will record answers and assess whether the person calling is likely or not to be an acceptable study participant. If the caller and the interviewer agree that the caller should participate, the prospective participant will be invited to a screening meeting, where the study will be fully described, and the individual will be provided a consent form to complete prior to any involvement in the study procedures. Data collected during this phase will include participant’s age, health status, physical activity, and contact information (see “*Informed Consent*” attachment).

3. Power Calculation and Data Analysis. [name] (biostatistician; *co-PI and Dept of Biomedical Informatics*) performed a power analysis. To ensure that the order by which each participant completes each trial is randomized, a random sequence generator (<http://www.random.org/sequences/>) will be used to determine the order by which each participant will undergo the two trials. We will primarily compare the

within-subject changes (WWB endpoint vs. WB endpoint) between high-responders and low-responders. We anticipate to have 6-12 high-responders and 5-10 low-responders of the total 40 study participants to achieve 80% power to detect a 1.6-fold difference in the changes of postprandial glucose levels (AUC from 0 to 180 minutes) between high-responders and low-responders, at the expected coefficient of variation (CV) 0.5 at a significant level of 0.05.

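### The primary high- versus low-responder test is powered on the glucose AUC change, the variable the plan points to for forming the groups; if they are formed on it, the test is circular and its 80% power figure has no meaning

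*Combined protocol and SAP*

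**What the plan says.** Section VI.B.3 (Power Calculation and Data Analysis) names the primary comparison as "within-subject changes (WWB endpoint vs. WB endpoint) between high-responders and low-responders". It anticipates 6-12 high-responders and 5-10 low-responders among 40 participants, "to achieve 80% power to detect a 1.6-fold difference in the changes of postprandial glucose levels (AUC from 0 to 180 minutes", at a CV of 0.5 and a significance level of 0.05. This is the only sample-size support in the document.

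No section gives a responder cut-off, percentile or algorithm. The descriptions of the groups are these:

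- Section II.D contrasts "subjects who exhibited improved glucose metabolism following the WWB diet with those who responded least to this dietary intervention".
- Section III expects postprandial glucose to fall by more than 25% on whole wheat bread (WWB) relative to white bread (WB) in high-responders. It refers to a "subset group of study participants who have larger changes of glycemic response post WWB intervention", and says the design aims to define the two groups "towards precision nutrition rather than achieve group mean differences by bread treatment".
- Section IV foresees difficulty in finding enough of each group "based solely on the glycemic responses". It adds a fallback: "If needed, we will combine other health parameters, such as HOMA-IR, serum endotoxin, and select inflammatory biomarkers, to define response indicators". No weights, cut-offs or trigger are given.

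On timing, Section VI.A says "Lastly, on day 14, participants will simultaneously complete an oral glucose tolerance test and gut permeability test". Sections VI.C.2, VI.D.1 and VI.D.3 agree: one glucose tolerance test per arm.

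**The concern.** One glucose tolerance test per arm gives each participant one WWB-WB difference in AUC. If that difference sorts people into high- and low-responders, comparing the same difference between the groups only confirms that they were sorted. The result would be significant whether or not bread does anything and whether or not true responders exist, so a reader could take a forced p-value as proof of both.

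The power statement falls with it. Power is the chance of detecting an effect that might be absent, and here the test would reject when it is absent. Because no other sample-size support is given, nothing would then be stated about what 40 participants can show on a question the trial can validly answer.

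**Working it through.** **Inputs.** From Section VI.B.3: 40 participants, 6-12 versus 5-10, 1.6-fold difference, CV 0.5, alpha 0.05 (sidedness not stated). From Sections VI.A and VI.C.2: one AUC per arm. Correlations, composites and within-person CVs below are assumptions, labelled as such.

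**1. The plan's own figure.** Read 1.6-fold at CV 0.5 as a difference of 0.6 with SD 0.5, two-sided normal approximation: power = Φ(0.6 / [0.5·√(1/n1 + 1/n2)] − 1.96).

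- 12 v 10: 0.6/0.2141 = 2.803; Φ(0.843) = 80.0%.
- 6 v 5: 0.6/0.3028 = 1.982; Φ(0.022) = 50.9%.

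The stated 80% is matched at the top of the range only. That is a separate matter. What counts here is that this formula assumes group membership is independent of the tested change.

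**2. Groups cut on the AUC change, any distribution.** A ranking or cut-off separates the groups completely (no ties), so the exact two-sided rank-sum p-value is 2/C(n1+n2, n2).

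| Groups | Calculation | p |
|---|---|---|
| 6 v 5 | 2/462 | 0.0043 |
| 9 v 8 | 2/24,310 | 0.00008 |
| 12 v 10 | 2/646,646 | 0.000003 |

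The maximum over all planned sizes is 0.0043.

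**3. t-test simulation.** 40 independent normal differences with mean zero and no responder subgroup, 20,000 runs, highest versus lowest on the difference: 100% rejection at 6 v 5, 9 v 8 and 12 v 10. It is also 100% when low-responders are those nearest zero, and 99.2-99.8% with heavy-tailed differences. With a true mean effect of 0.5 SD, or true heterogeneity as large as the noise, it is again 100%, so the test cannot tell these situations apart. With group labels independent of the change, rejection is about 5%.

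**4. Grouping on something else.** No bread effect in any row.

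| Situation (assumed) | Rejection, 6 v 5 to 12 v 10 |
|---|---|
| Groups on AUC, tested variable uncorrelated with it (such as an unrelated microbial feature) | about 5% |
| Groups on AUC, related measure tested, correlation 0.3 | 30-37% |
| The same, correlation 0.5 | 72-83% |
| Composite of AUC and 1 uncorrelated marker, AUC tested | 98-99.6% |
| Composite with 2 markers | 86-93% |
| Composite with 3 markers | 73-83% |

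The correlation rows reflect a real correlation. They mislead only if read as a bread effect or as responder heterogeneity.

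**5. Would the planned groups be obtained?** Take the 25% fall as an illustrative fixed cut-off with no bread effect. For log-normal AUCs, P(fall > 25%) = Φ(ln 0.75 / √(2·ln(1+CV²))).

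| Within-person CV (assumed) | P | Expected in 40 | Chance of at least 6 |
|---|---|---|---|
| 0.10 | 0.021 | 0.8 | 0.02% |
| 0.15 | 0.086 | 3.5 | 13% |
| 0.20 | 0.152 | 6.1 | 58% |
| 0.25 | 0.204 | 8.2 | 85% |

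**6. A comparison that is not circular.** For the paired WWB-WB log-AUC difference in 40 completers, adjusted for period (noncentral t, 38 df, noncentrality d·√40), d = 0.455 gives 80% power at two-sided 0.05; unadjusted, d = 0.454. The detectable mean change is 1 − exp(−0.455·√(2·ln(1+CV²))): 6, 9, 12, 15 and 26% at within-person CVs of 0.10, 0.15, 0.20, 0.25 and 0.50. The documents give no within-person CV. Their only glucose CV is 0.5, and what it refers to is not stated.

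**The case against.** The strongest reply is that the circularity is inferred: Section VI.B.3 never says the groups are formed on the AUC change. That is true, and a reader should not infer that the plan prescribes it. Section II.D speaks of glucose metabolism in general, fasting glucose and insulin are also measured, and Section IV allows a composite. So the point stays conditional. Still, every description of the groups starts from the glycemic response, and the one figure attached to high-responders, the 25% fall, concerns postprandial glucose. That figure is worded as an expectation and defines no low-responder; used as the rule, it would be just as circular.

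A second reply is that significance is not guaranteed, and this stands in part. Section IV's worry about finding enough responders suggests a fixed cut-off rather than a ranking, and step 5 shows that at low noise such a cut-off would seldom yield six high-responders by chance. The planned test might then not be possible. Under such a cut-off the informative quantity would be the number of responders; it does not rescue the p-value once the groups exist.

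A third reply is that the scientific weight lies on the microbiota, and that Section VI.B.3 already has a mixed model with diet as a fixed factor. Both are right, and both limit the damage to the glucose contrast. Yet that contrast carries the document's only power claim, within a comparison called primary.

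**Conclusion.** The concern holds in conditional form. If responder groups are formed on the AUC change, then whenever groups of the planned size are obtained the between-group AUC test rejects in about 100% of null datasets (rank-sum p at most 0.0043). It is then not evidence of a bread effect or of responders, and the 80% figure has no meaning for it. The Section IV composite reduces the problem without removing it: 73-99.6% under the assumption of one to three uncorrelated markers.

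Two stronger readings are not supported. One is that the whole responder approach fails: comparisons of microbiota or metabolites not used for grouping, and the diet effect in all participants, are not affected in this way. The other is that the trial must switch to the mean bread effect as its primary question: Section III argues openly against that aim, and the choice is the sponsor's.

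The 100% result rests on grouping by the tested change. The missing rule and the single glucose tolerance test per arm are facts of the documents.

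**What to change.** 1. State the responder rule before the data are seen: variable, cut-off or ranking, definition of low-responder, and the trigger and weights for any composite.
2. Report the AUC change by responder group descriptively, with no p-value, and withdraw the 80% power statement attached to it.
3. Add wording such as: *Variables used to form the responder groups, including any composite components, and closely related glycemic measures will not be tested between the groups as evidence of a bread effect or of responder heterogeneity.*
4. Restate the sample-size support for a comparison that is not circular. One example is the paired AUC difference in all completers under the diet mixed model already planned: 80% power for a standardized difference of about 0.45 with 40 completers, shown over the full CV range in step 6, including 0.50.

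Optional: adjust for period (the model's time factor is undefined and could mean period), and add the association of microbiota features with the continuous AUC difference. These are preferences, not corrections.

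The cost is a few sentences and a restated power paragraph, with no added participants, visits or assays. The p-value given up carries no information under AUC-based grouping.

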Mixed effect modeling will be performed, diet and time will be included as fixed factors while participant serves as a random factor. False discovery rate (FDR) will be used to control type I error rate for microbiome and metabolome data, while the Bonferroni method will be applied for other measures (e.g., inflammatory markers). Data will be first normalized before analysis. Spearman correlations will be calculated to define associations between microbes, inflammatory genes, metabolites that show significant changes in highresponders.

To test whether the changes in microbes after WWB intake associate with the biological response, logistic regression will be fitted to each of the potential microbes or as a combination. We will also couple the logistic regression with receiver-operating characteristic (ROC) analysis to evaluate the specificity and sensitivity of the microbes that predict participants' biological response, and the area under the curve (AUC) of the microbial model will be displayed. Data analysis will be performed in R (open resource) or SAS (SAS, Inc; Cary, NC). The sample size was calculated in PASS 20 (NCSS, LLC; Kaysville, Utah).

C. Measurement/Instrumentation

All procedures will take place in the Human Nutrition Program located in Evans Laboratory. Infrastructure that is present includes a metabolic research kitchen, a private office to meet with participants, a clinical research laboratory for performing phlebotomy and research procedures, and a separate biochemical laboratory for processing and preserving biological specimens.

1. *Anthropometric Parameters and Blood Pressure.* At screening, day 1, 7, and 14, participants will rest for 15 minutes prior to determining blood pressure using an automated blood pressure cuff. BMI will be calculated from height determined from a wall-mounted stadiometer and weight from a calibrated scale.

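### The single 80% power figure does not hold across 6-12 versus 5-10 responders: a two-sided t-test on the plan's inputs gives 31-60% (log scale) or 42-76% (raw scale)

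*Combined protocol and SAP*

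**What the plan says.** Section VI.B.3 (Power Calculation and Data Analysis) makes the main comparison one of within-subject change, whole wheat endpoint against white bread endpoint, between high- and low-responders. On numbers it says: "We anticipate to have 6-12 high-responders and 5-10 low-responders of the total 40 study participants". These are to give "80% power to detect a 1.6-fold difference in the changes of postprandial glucose levels (AUC from 0 to 180 minutes"), "at the expected coefficient of variation (CV) 0.5 at a significant level of 0.05".

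The same section adds "The sample size was calculated in PASS 20" and "Data will be first normalized before analysis". It does not name the test, the analysis scale, one- or two-sidedness, the quantity to which the CV applies, or the pair of group sizes that gives 80%.

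Two other sections bear on this. Section III says the design is aimed at defining responders "towards precision nutrition rather than achieve group mean differences by bread treatment". Section IV warns that "there may be difficulties to identify sufficient" responders of each kind on glycemic response alone.

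**The concern.** Power depends on group size, and 12 versus 10 is twice 6 versus 5. A single figure of 80% can be right for some sizes in that range but not for all of them. The inputs (1.6-fold, CV 0.5, 0.05) also looked too weak to give 80% with so few responders.

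The responder comparison is the stated purpose of the trial, and no other power calculation is given. If few responders are found, which Section IV treats as possible, a null comparison would be read against a claimed 80% chance of detection when the nominal chance is far lower.

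**Working it through.** **Inputs from Section VI.B.3.** High-responders n1 = 6 to 12 and low-responders n2 = 5 to 10, so 7 × 6 = 42 size pairs; ratio 1.6; CV 0.5; significance level 0.05. The groups are separate people, so the natural test is a two-sample comparison. Test, scale and sidedness are my assumptions, and I varied them.

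**Step 1: can one figure fit the range at all?** This needs no assumption about scale. For a two-sided t-test, the standardized difference d that gives 80% at 12 versus 10 is 1.261, and it gives 46% at 6 versus 5. The d that gives 80% at 6 versus 5 is 1.907, and it gives 99% at 12 versus 10. So no effect size gives 80% at both ends.

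**Step 2: standardized difference from the plan's inputs.**
- Log scale: SD = √ln(1 + 0.5²) = √ln 1.25 = 0.472; d = ln 1.6 / 0.472 = 0.470 / 0.472 = 0.995.
- Raw scale, SD = 0.5 × low-responder mean: d = (1.6 − 1) / 0.5 = 1.2.
- Raw scale, CV 0.5 in each group: SDs 0.5 and 0.8 × the low-responder mean; pooled SD = √[(0.25 + 0.64)/2] = 0.667; d = 0.6 / 0.667 = 0.90.

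**Step 3: power.** Noncentral t with df = n1 + n2 − 2 and noncentrality d × √[n1·n2/(n1 + n2)]. The square-root term is 1.651 at 6 versus 5 and 2.335 at 12 versus 10. On the raw scale with d = 1.2 the noncentrality is therefore 1.98 and 2.80, against two-sided critical values of 2.262 (9 df) and 2.086 (20 df).

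| Reading | 6 vs 5 | 9 vs 8 | 12 vs 10 | Pairs at ≥80% (of 42) |
|---|---|---|---|---|
| Two-sided t, log | 31.2% | 48.3% | 59.9% | 0 |
| Two-sided t, raw, d = 1.2 | 42.5% | 63.7% | 76.0% | 0 |
| Two-sided t, raw, d = 0.90 | 26.5% | 41.0% | 51.6% | 0 |
| Two-sided normal, log | 37.6% | 53.5% | 64.2% | 0 |
| Two-sided normal, raw, d = 1.2 | 50.9% | 69.5% | 80.0% | 1 |
| One-sided t, log | 45.0% | 62.1% | 72.5% | 0 |
| One-sided t, raw, d = 1.2 | 57.4% | 76.2% | 85.6% | 8 |
| One-sided normal, raw, d = 1.2 | 63.2% | 79.5% | 87.7% | 13 |

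**Step 4: where the plan's 80% reproduces.** A raw-scale two-sided normal approximation gives 80.0% at exactly 12 versus 10. The raw-scale one-sided t-test reaches 80% only in pairs with at least 19 responders in total. At 6 versus 5, no row exceeds about 63%.

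**Step 5: what the sizes can support** (two-sided t, 80% power). With d = 1.907 at 6 versus 5 and 1.261 at 12 versus 10:
- Detectable fold, raw = 1 + 0.5d: 1.95 and 1.63.
- Detectable fold, log = exp(0.472d): 2.46 and 1.81.
- Largest CV that keeps 80% for 1.6-fold: raw 0.31 and 0.48; log 0.25 and 0.39.

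A simulation of 200,000 runs agrees for the two-sided t-test: log 31.4% and 59.8%, raw 42.5% and 75.9% at the two ends.

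**The case against.** The plan names no test, scale or sidedness, so every percentage above rests on a chosen model. The stated 80% does reproduce at the top of the range under one such model. The calculation may have been run at 12 versus 10 and its result attached to the whole range, which would make this a reporting slip and not a wrong calculation. Even the raw two-sided t-test gives 76% there, with a detectable ratio of 1.63 against the stated 1.6. This stands as far as it goes: the documents cannot show which procedure was used, and on the raw scale the shortfall at 12 versus 10 is small. The raw scale is also at least as plausible as the log scale, since a signed change can be zero or negative.

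Other readings of the effect size give more power. Taking 1.6 as the standardized difference itself gives 65% at 6 versus 5 and 94% at 12 versus 10 (two-sided t). With a one-sided normal approximation it gives 84% to 98%, above 80% throughout. That reading leaves the stated CV without a role, does not fit the fold wording, and applies a large-sample formula to 11 people. Taking the difference as 1.6 times the mean (d = 3.2) gives over 99%, which is not 80% either.

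Two further points are fair. If responders are picked on glycemic response and then compared on glucose AUC, a difference is more likely than these nominal figures suggest. That is a separate problem with the comparison and does not support the 80%. Section IV also offers other markers for defining response if too few responders are found, but this does not restore power for the glucose endpoint as stated.

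**Conclusion.** The concern holds. Whatever test was used, one figure of 80% cannot describe both 6 versus 5 and 12 versus 10. Reading 1.6-fold as a ratio of mean changes with CV 0.5, every variant tried falls short in the lower part of the range. With a two-sided t-test the shortfall at 6 versus 5 is about 38 to 49 percentage points (42% raw, 31% log). At 12 versus 10 it is 4 points on the raw scale and 20 on the log scale.

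Confidence is high that the single figure is unsupported. The specific percentages depend on the assumed test and scale and on the SD reference: applying the CV to both groups lowers the raw-scale range to about 26-52%. Because this is the sole power justification for the main comparison, it must be corrected.

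**What to change.** In Section VI.B.3, name the test, the scale, the sidedness and the quantity to which the CV of 0.5 applies. Replace the single 80% with power at both ends of the range, or with the fold difference detectable at 80% power. The wording depends on the procedure actually run:

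- Two-sided t-test, raw scale, SD = 0.5 × low-responder mean: power for a 1.6-fold difference is 42% (6 versus 5) to 76% (12 versus 10); the difference detectable with 80% power is 1.95-fold to 1.63-fold.
- Two-sided t-test, log scale: power is 31% to 60%; the detectable difference is 2.46-fold to 1.81-fold.
- If the PASS run was one-sided or used a normal approximation, say so and still give the 6 versus 5 figure (raw scale: 57% for the one-sided t-test, 51% for the two-sided normal approximation).

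The cost is one paragraph of text, with no added participants and no change to procedures. The stated power becomes less favourable.
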